8.3 EVALUATIONS

When evaluating AEs, the Investigator must determine if the event is serious, assess the severity of symptoms, the relationship of the event to the device or study protocol, using the following guidelines:

1. Severity

Mild: subject awareness of a sign or symptom that is easily tolerated, requires no treatment, and does not interfere with subject's daily activities

Moderate: subject awareness of a sign or symptom which may be a low level of concern to the subject and may interfere with daily activities, but can be relieved by simple therapeutic care

Severe: a sign or symptom that interrupts the subject's daily activity and requires systemic therapy or other treatment

2. Relationship (Causality) to Study Device or Study Protocol

Related: There is at least a reasonable possibility that the AE/SAE is related to the study device or study protocol. Reasonable possibility means that there is evidence to suggest a causal relationship between the study device or study protocol and the AE. **Unrelated:** There is little or no reasonable possibility that the AE/SAE is related to the study device or study protocol. This assessment implies that the AE/SAE has little or no temporal relationship to the study device and/or a more likely or certain alternative etiology exists.

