3 STUDY OBJECTIVE

The primary objective of this study is to conduct a post-approval study which evaluates the following two safety questions:

- 1. What is the rate of Endothelial Cell Density loss (ECL) for patients with the RxSight LAL/LDD?
- 2. What is the rate of retinal damage caused by UV treatment with the LDD that may not be detected by routine post-operative testing?

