6.9.1 SUBJECT COMPLETION

Subjects are considered to have completed the study if they have completed the Postop Month 6 examination unless the subject is diagnosed with retinal phototoxicity. In that case, a Month 12 examination will be conducted for the RxSight LAL group only to confirm resolution or document sequelae, if any.

Subjects with ocular serious adverse events or adverse device effects that are unresolved at study exit should continue to be followed until resolution of the event or until they are stable per the investigator's evaluation.

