7.6.3 Additional Safety Analyses

The following safety outcomes will be summarized descriptively based on the observed data and actual lens implanted. Results will be presented for all the RxSight LAL eyes and the Control group eyes. The 95% confidence intervals for means or percentage may be presented, as appropriate.

Adverse Events

Number and percent of study eyes will be summarized for each reported ocular AE at the operative visit and each postoperative visit for the LAL group and Control group separately. Serious ocular AEs and the non-ocular serious AEs will be summarized in the same manner. Additionally, for each of the device related AE reported during the study, the number and

percent of study eyes reported with the event will be presented. The ocular adverse events will be listed for eyes, if applicable, with IOL implantation attempted but without implantation. Ocular adverse events will be reported separately for the fellow eye.

BCDVA

BCDVA will be presented with the number and percent of eyes who fall into each category of BCDVA at each visit (e.g. 20/20 or better, 20/25 or better, 20/32 or better, etc.). The mean and standard deviation (SD) of BCDVA letter score will also be calculated for each visit. Change in BCDVA from Postop Week 3 or from Preoperative will be presented at each visit as categorical outcomes of "Increase in 15 letters or more", "Increase in 10-14 letters", "Increase in 5-9 letters", "No change", "Decrease in 5-9 letters", "Decrease in 10-14 letters", and "Decrease in 15 letters or more The mean and SD of the change from Postop Week 3 or Preoperative will also be presented. Similarly, the mean change from the prior visit to the next visit will also be summarized in the same manner.

In-Office Erythropsia Assessment (RxSight LAL only)

The number and percent of eyes in each outcome of erythropsia assessment (0- white, 1-pink, or 2- red) will be presented. In addition, the number and percent of eyes with increases in the level of erythropsia from the Postop Week 3 visit will be presented.

Daily Life Erythropsia Questionnaire (RxSight LAL only)

Results of the Daily Life Erythropsia Questionnaire will be summarized descriptively at each visit the questionnaire is completed.

City University Color Test (RxSight LAL only)

[figure not shown]
Results of the City University Color Test will be reported as the number and percent of eyes that have tritan findings >1 on Part Two of the test.

Slit Lamp Examinations

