8.1 ADVERSE EVENT DEFINITIONS

An adverse event (AE) is any untoward medical occurrence, unintended disease or injury, or untoward clinical signs (including abnormal laboratory findings) in subjects, users, or other persons, whether or not related to the investigational medical device.

Note 1 to entry: This definition includes events related to the investigational medical device or the comparator.

Note 2 to entry: This definition includes events related to the procedures involved.

Serious Adverse Events (SAEs) are AEs that lead to:

- death
- a serious deterioration in the health of the subject that:
 - results in a life-threatening illness or injury
 - results in a permanent impairment of a body structure or function (e.g., blindness)
 - requires in-subject hospitalization or prolongation of existing hospitalization
 - results in medical or surgical intervention to prevent permanent impairment to a body structure or a body function
- fetal distress, fetal death, or a congenital abnormality or birth defect
- a potentially sight-threatening condition
- or is another important medical event.

MDR reportable event: An event that manufacturers become aware of that reasonably suggests that one of their marketed devices:

- · May have caused or contributed to a death or serious injury, or
- Has malfunctioned and that the device or a similar device marketed by the manufacturer or importer would be likely to cause or contribute to a death or serious injury if the malfunction were to recur.

Serious injury means an injury or illness that:

- · Is life-threatening,
- Results in permanent impairment of a body function or permanent damage to a body structure, or
- Necessitates medical or surgical intervention to preclude permanent impairment of a body function or permanent damage to a body structure. Permanent means irreversible impairment or damage to a body structure or function, excluding trivial impairment or damage.

The following may be considered normal events after cataract surgery and only need to be reported as AEs as specified:

- Iritis/cells/flare (if present after Postop Week 1 and greater than grade 1 (trace)) or (any iritis/cells/flare present at Postop Month 6 of any grade)

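### The single AE causality judgement in Section 8.3 joins device and protocol, so the device-related AE table in Section 7.6.3 has no defined numerator (minor)

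*Combined protocol and SAP*

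**What the plan says.** Section 8.3 sets the investigator's task as judging "the relationship of the event to the device or study protocol, using the following guidelines". There are two levels. Related is explained as: "There is at least a reasonable possibility that the AE/SAE is related to the study device or study protocol". Under Unrelated the text adds: "This assessment implies that the AE/SAE has little or no temporal relationship to the study device", and/or that another cause is more likely or certain.

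Section 8.1, Note 2, says of the AE definition: "This definition includes events related to the procedures involved". Note 1 brings in events related to either the investigational device or the comparator.

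Section 7.6.3 tabulates all ocular AEs by visit and by arm. It then adds counts and percentages of eyes "for each of the device related AE reported during the study". It does not say how device related is determined.

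Section 6.9.1 states: "Subjects with ocular serious adverse events or adverse device effects that are unresolved at study exit should continue to be followed until resolution", or until stable in the investigator's evaluation. Section 8.1 does not define adverse device effects.

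**The concern.** The field that is collected and the table that is planned do not match. The field joins device and protocol; the table needs device alone. In the LAL arm, *study device* could also mean the implanted lens, the LDD or both. In the Control arm it is unclear whether an event due to the monofocal IOL counts.

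This matters because Phase B is a post-approval safety study. Section 3 asks: "What is the rate of retinal damage caused by UV treatment with the LDD that may not be detected by routine post-operative testing". Section 11 provides for public posting of interim analyses that include safety summaries. Readers will take a device-related table to mean what it says. If its rows mix lens, light and surgical causes, or depend on how each of up to 15 sites reads 8.3, it cannot be interpreted that way.

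**Working it through.** The plan gives no figure for device-related AEs (no rate, power or precision), so there is nothing to reproduce. The check sets the sections side by side.

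**Step 1. Trace each source of an event through the 8.3 judgement.**

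| Source of the event | Result under 8.3 | Does a device-only table need it? |
|---|---|---|
| Implanted lens | Related (device) | Yes |
| LDD light treatment | Related (device) | Yes, and identifiable as light |
| Cataract surgery | Related if surgery counts as protocol; Unrelated if it counts as another cause | No |
| Other study procedure | Related (protocol) | No |

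The Related level can hold all four sources, and nothing in the text separates them afterwards. Filtering on Related therefore does not give a device-only set.

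**Step 2. Test the two definitions on one event.** Take corneal edema after phacoemulsification. Surgery is performed under the protocol in both arms (6.4.1, 6.5), and procedure-related events are AEs (8.1, Note 2), so Related is defensible. Surgery is also a likelier cause than the device, so Unrelated is defensible. The wording permits both answers because Related names device or protocol, while the timing test under Unrelated names the device only.

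**Step 3. Find which rows of the table are exposed.** Section 7.6.3 works by event term. A term that only one source can cause stays interpretable whatever the field says. The exposed terms are shared ones. Section 8.6 lists corneal edema and iritis as potential events of any cataract surgery. Section 8.1 makes both reportable according to grade and persistence after Postop Week 1 (Days 7 to 14), among other conditions. By the visit windows in 6.6:

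- First light treatment: Days 17 to 24.
- Earliest end (one adjustment, one lock-in): 17 + 3 = Day 20.
- Latest end (three adjustments, two lock-ins, so four intervals of at most 7 days): 24 + 4 × 7 = Day 52.

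Persistent surgical edema or iritis can thus be present throughout light treatment. Each treatment also places a contact lens on the cornea (6.4.2.4, 6.4.2.5). Timing alone does not settle the cause of such an event.

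**Step 4. See whether other analyses supply the attribution.** The LAL-versus-Control contrast removes what surgery contributes to both arms but leaves lens and light together. Detection also differs: LAL eyes can have four more scheduled visits (Adjustments #2 and #3, Lock-ins #1 and #2), and erythropsia and color testing are done in LAL eyes only. The UV-damage endpoint concerns the retina. MDR review (8, 8.1) is limited to death, serious injury and certain malfunctions. None of these attributes a shared anterior-segment term.

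**The case against.** Several counter-arguments have force.

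- **The table is by event term.** A reader might infer that surgical events dilute an LDD signal across a pooled rate. Section 7.6.3 plans no pooled device-related rate. Wound leak and erythropsia would be on different rows, so mixing can occur only within a shared term. This stands, and it narrows the point.
- **Surgery is not expressly part of the study protocol for causality.** A reader might infer that 8.3 makes every phacoemulsification complication Related. It does not say so: Note 2 in 8.1 defines what an AE is, not how to judge cause, and the Unrelated text allows another etiology. What stands is ambiguity, not a fixed misclassification.
- **LDD harm is addressed elsewhere.** A reader might infer from the Section 3 question that the study cannot assess harm from light. The documents do not support that. UV retinal damage in LAL eyes is a primary safety endpoint (5.2), with triggered testing (6.4.2.2) and independent expert review (synopsis). Tritan increase and erythropsia are AEs referenced to Week 3, the visit of the first light treatment (8.1). All ocular AEs are tabulated by visit and arm whatever their cause, and an event before the first light treatment cannot be due to LDD light.
- **The AE form is not in the documents, and 7.2 defers detail to a later SAP.** The form may already split causality. If so, 8.3 and 7.6.3 should say so. If not, a later SAP can define a table but cannot recover an attribution that was not collected.
- **Follow-up under 6.9.1 would err toward caution.** Reading surgical events as device effects would extend follow-up, and ocular SAEs are followed whatever their cause. This is fair; what remains is an undefined term.

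**Conclusion.** The mismatch is real, and minor. Followed as written, 8.3 yields a Related category that can mix lens, light and procedure effects, and its two definitions can give opposite answers for one surgical event. The device-related table in 7.6.3 and the term adverse device effects in 6.9.1 therefore have no defined content.

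The effect is limited to that table, chiefly to rows for terms with more than one possible cause. Neither primary safety endpoint depends on the causality field, and nor do the effectiveness summaries. No magnitude can be given, because the documents state no event rates or expected number of related AEs.

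This rests on three assumptions: that the AE form follows 8.3 as worded; that sites may reasonably read study protocol as including the surgery; and that terms such as corneal edema and iritis can arise from surgery, lens or light.

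**What to change.** 1. In 8.3 and on the AE form, record relationship separately for the implanted lens (LAL or Control IOL), LDD light treatment, cataract surgery, and other study procedures.
2. Align the Related and Unrelated wording so that each judgement is made against the same named source.
3. In 7.6.3, define device related as related to the implanted lens or to LDD light treatment, in both arms, and show LDD-light-related events separately.
4. Reconcile adverse device effects in 6.9.1 with these definitions.

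The cost is a few more items on the AE form, one further table, minor extra site work, and requery of AEs already entered. The change is best made early, since retrospective attribution is less reliable. If the form already collects these items, only the protocol text needs to change.

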8.4 SAE REPORTING

The site should report any event to the Sponsor and its representative in an expedited manner if it meets the criteria for an SAE and/or is an IOL explant from a study eye. Expedited reporting is calling or e-mailing the Sponsor and its representative within 48 hours of becoming aware of the event. When reporting an SAE to the Sponsor and/or its representative, the site should forward any supporting documents along with the SAE Report Form to the Sponsor and its designee within 5 days of the initial communication. Sites must also report these events to the reviewing IRB/IEC per its established reporting procedures.

8.5 Pregnancy

During the study, all female subjects of childbearing potential should be instructed to contact the investigator immediately if they suspect they might be pregnant (e.g., missed or late menstrual period). Female subjects who become pregnant during the study will be followed until completion of pregnancy. Every effort will be made to obtain the health status of the mother and infant or fetus (in cases of miscarriage or therapeutic abortion) at term. Pregnancy itself is not considered an AE.

All confirmed pregnancies must be immediately reported to the Sponsor within 48 hours of the investigator's awareness of the pregnancy.

8.6 POTENTIAL ADVERSE EVENTS

[figure not shown]
The following have been identified as potential adverse events for all cataract surgeries including the RxSight LAL and the control IOL. Please notify the Sponsor regarding any events that may be occurring more frequently than your customary rates, or more frequently than expected at your site.

Infection (endophthalmitis), hypopyon, infectious keratitis, hyphema, inflammation, corneal endothelial damage, IOL dislocation out of the posterior chamber, cystoid macular edema or other retinal problems including and epiretinal membranes, toxic anterior segment syndrome, striation on the lens with or without visual sequelae, iritis, synechiae, ptosis, wound leak, flat anterior chamber, increased astigmatism, vitreous in the anterior chamber, retained pieces of the lens in the eye, corneal edema, pupillary block, retinal detachment, transient or persistent glaucoma, vitritis, iris prolapse, rupture of the capsule, and secondary surgical intervention. Increased visual symptoms related to the optical characteristics of the IOL include: halos, glare, and/or double vision.

Secondary surgical interventions include, but are not limited to: lens repositioning, lens replacement, vitreous aspirations or iridectomy for pupillary block, lysing of synechiae, wound leak repair, retinal detachment repair and corneal transplant.

These adverse events may result in total loss of vision or the loss of an eye.

Additionally, a posterior capsulotomy may be required to treat posterior capsular haze after the cataract surgery. These and other complications may result in permanent poor vision.

9 STUDY MONITORING

RxSight clinical personnel or designated CRO will monitor all clinical studies in a manner consistent with any applicable health authority regulations and the clinical research standards adopted by RxSight's Clinical Affairs Department. Study monitoring will involve the following elements:

- Member(s) of RxSight's Clinical Affairs Department or designated CRO may meet
 with investigators prior to the initiation of the study in order to review the adequacy
 of the subject population, facilities, and equipment with respect to the needs of the
 study, and to familiarize the investigator with the study protocol. This evaluation
 may be performed remotely.
- A member of RxSight's Clinical Affairs Department or designated CRO may meet with the investigator(s) at the time study subjects begin to be enrolled in order to ensure that subjects are being properly selected and that study data are being correctly recorded. These meetings and assessments may be performed remotely.
- A member of RxSight or designated CRO may visit the clinical site at any time during the study to review study worksheets and data entered in the EDC system. Remote review of study worksheets, case histories and other data (including data with PHI) may be reviewed remotely.
- Interim monitoring visits and telephone consultations will occur as necessary during the course of the study to ensure the proper progress and documentation of the study findings. Centralized and/or remote monitoring may be performed during the conduct of the study. Interim monitoring visits may be performed remotely; this includes remote review of study worksheets, case histories and other data which may contain PHI.
- RxSight clinical personnel may visit the site at any time during the course of the study to observe implantation of the RxSight LAL and the adjustment and lock-in treatments to ensure that the procedures described in the protocol are being followed. Visits by RxSight clinical personnel may occur via video conferencing.
- RxSight clinical personnel may also observe examination techniques used by study personnel to ensure that the procedures being utilized are the procedures described in . RxSight clinical personnel may also observe examination techniques via video conferencing.

10 ETHICAL AND REGULATORY CONSIDERATIONS

10.1 SUBJECT INFORMATION AND CONSENT

It is the responsibility of the Principal Investigator or authorized designee to give each subject prior to inclusion in the study full and adequate verbal and written information regarding the objective and procedures of the study and the possible risks involved. The subjects will be informed about their right to refuse to participate in the study. The written consent form will be given to each subject before enrollment. It is the responsibility of the Principal Investigator to obtain a signed informed consent form and a HIPAA consent form and to ensure the subject is given a copy of each.

The Principal Investigator or authorized designee needs to file the informed consent forms for review by RxSight study monitors. The Investigator or authorized designee will acknowledge the receipt of the informed consent form from each subject by signing the appropriate pages of these documents.

10.2 DECLARATION OF HELSINKI

The study will be performed in accordance with the relevant recommendations guiding physicians in biomedical research involving human subjects adopted by the 18th World Medical Assembly, Helsinki, Finland, 1964 and later revisions, as well as applicable U.S. Food and Drug Administration regulations (21 CFR Parts 50, 56, and 812).

It is the responsibility of the Principal Investigator to obtain Institutional Review Board approval of the Study Protocol and to keep the IRB informed of serious side effects or adverse events and any amendments to the protocol.

[figure not shown]
10.3 ADDITIONAL REGULATORY CONSIDERATIONS

The proposed study is subject to all applicable governmental rules and regulations concerning the conduct of clinical trials on human subjects. This includes, but is not necessarily limited to, the approval of an Institutional Review Board (where applicable); obtaining prospective informed consent; monitoring of the conduct of the study, the completeness of the study worksheets, and accuracy of data entered into the EDC system, as may be employed, by the Sponsor or its designee(s); and record retention by the Sponsor in accordance with 21 CFR Subpart G-Records and Reports.

11 REPORTING REQUIREMENTS

An interim report will be submitted every 6 months for the first 2 years of the study and then annually thereafter, from the date of the approval of the PMA Supplement. The interim analyses will be posted on the FDA post-approval website for public access. Descriptive analyses will be provided including subject enrollment, demographic data, follow-up rate, and summary measurements for safety and effectiveness defined the same as in the final report.

